2.3. Secondary Objectives

- Evaluate the safety and tolerability of IMGN853
- Evaluate the effectiveness of primary, prophylactic steroid eye drops in preventing or lessening keratopathy and/or blurred vision
- Characterize the PK of IMGN853 when administered intravenously
- Describe any preliminary evidence of IMGN853 antitumor activity
- Characterize the immunogenicity of IMGN853

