5.8.8. Monitoring and Management of Treatment-emergent Eye Disorders

5.8.8.1. Monitoring - Potential Ocular Disorders

Changes in visual acuity, resulting from reversible keratopathy have been reported in other studies of DM4-containing immunoconjugates that use the SPDB linker (Younes 2012). Due to the observation of ocular disorders in patients treated with IMGN853 at the 5.0 and 7.0 mg/kg dose levels, (Section 1.9) ocular function is being carefully monitored. Complete ophthalmologic exams and ocular symptom assessments will be performed in all patients at baseline and post-treatment as described in the following schedule:

Table 7: Schedule for Ophthalmologic Assessments

Assessment	Screening	Day 1 (All Cycles)	Prior to Day 1 Dose (Every other Cycle) ⁴	End of Treatmen t	28-Day Follow Up
Ophthalmologic history – patients will be asked about ocular symptoms such as history of dry eye, and contact lens use	X				

ImmunoGen, Inc. Confidential Page 69 of 138

Assessment	Screening	Day 1 (All Cycles)	Prior to Day 1 Dose (Every other Cycle) ⁴	End of Treatmen t	28-Day Follow Up
Complete Exam ¹ : - Visual acuity (with/without corrective lenses; whichever best reflects the patient's usual functioning) - Slit lamp examination - Intraocular pressure measurement - Indirect fundoscopy	X^2		Patients who report treatment- emergent ocular AEs	X	X
Schirmer's test ⁴	X				
Ocular symptom assessment (blurred vision, ocular discomfort, etc.)	X	X		X	X
Prescribe 1% prednisolone (Cohort 5 Patients Only) ⁵	X				

¹ Performed by a board-certified ophthalmologist

If a subject develops ocular symptoms of any grade, the subject will be referred to an ophthalmologist for a complete examination. If a subject develops ≥ Grade 2 ocular symptoms, treatment with IMGN853 will be interrupted. In patients with clinical benefit, therapy may resume if ocular symptoms improve to Grade 1 or baseline within 21 days of the next scheduled IMGN853 dose. Subsequent examinations will be scheduled to occur in every other cycle going forward, from the time that the AE was initially reported, and at either the end of study or 28-day follow up visit. In the event of therapy being held for more than 14 days due to ocular symptoms, a subject showing clinical benefit prior to the onset of an ocular treatment-emergent adverse event may be allowed to resume therapy at a reduced dose after approval from the Sponsor.

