10.7. End of Treatment Visit

Patients may voluntarily withdraw from the study treatment at any time for any reason, and without prejudice to further treatment. In addition, patients may be withdrawn by the Investigator if they do not feel the patient is deriving clinical benefit or because the patient is experiencing unacceptable toxicity. The reasons for which a patient may be prematurely discontinued are listed in Section 5.10.

Patients who withdraw or are removed from the study treatment will have an end of treatment visit within 7 days of the decision to discontinue study treatment. All study evaluations described below will be performed. Additionally, these patients will undergo a 28-day follow-up safety visit. The eCRF will capture reasons for withdrawal.

The procedures listed below are to be undertaken at the end of treatment visit and documented in the eCRF:

- Symptom-directed physical examination (Appendix A and Appendix B)
- Vital signs as outlined in Section 8.6, Appendix A and Appendix B
- Pulse oximetry (Section 8.8) Weight (Appendix A and Appendix B)
- ECOG performance status (Appendix A and Appendix B)
- Clinical laboratory tests (Section 8.10, Appendix A and Appendix B):
 - Serum chemistry
 - Hematology
- Blood sample for measurement of homocysteine and methylmalonate as outlined in Section 7.2.3 and Appendix C
 - Ophthalmic examinations: visual acuity, fundoscopic exam, ocular symptom assessment (Section 5.8.8)
 - Single, 12-lead ECG (Section 8.7)
 - Radiologic imaging to monitor tumor response if PD has not been documented already (Appendix A and Appendix B)

ImmunoGen, Inc. Confidential Page 103 of 138

 CA125 - for patients with EOC, primary peritoneal cancer, fallopian tube cancer or uterine cancer (Appendix F)

NOTE: patients experiencing CA125 response must have a confirmatory test performed at least 28 days after initial response is documented.

- AEs and SAEs (Appendix A and Appendix B)
- Ocular symptom assessment (Section 5.8.8)
- Concomitant medications (Appendix A)
- HAHA and HADA sample collection as outlined in Section 6 and Appendix C

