10.8. Follow-up Assessments

Safety Follow-up: A safety follow-up visit will occur 28 days (+ 14 days) after the last treatment. During this visit, the following assessments will be performed.

- Complete physical examination (Appendix A and Appendix B)
- Vital signs (Section 8.6, Appendix A and Appendix B)
- Pulse oximetry (Section 8.8)
- Weight (Appendix A and Appendix B)
- ECOG performance status (Appendix A and Appendix B)
- 12-Lead ECG (if clinically indicated)
- Pregnancy test for WCBP (Appendix A and Appendix B)
- Clinical laboratory tests (Section 8.10, Appendix A and Appendix B):
 - Serum chemistry
 - Hematology
 - Coagulation profile
 - Urinalysis
- Radiologic imaging to monitor tumor response if PD has not been documented already (Appendix A and Appendix B)
- For patients with EOC, uterine cancer or NSCLC only:
- CA125 for patients with EOC, primary peritoneal cancer, fallopian tube cancer or uterine cancer (Appendix F)

NOTE: patients experiencing CA125 response must have a confirmatory test performed at least 28 days after initial response is documented.

- AEs and SAEs (Appendix A and Appendix B)
- Ocular symptom assessment (Section 5.8.8)

ImmunoGen, Inc. Confidential Page 104 of 138

- Complete ophthalmic examination for all patients; alternatively, the complete examination can be performed at the End of Study visit.
 - Patients experiencing an ocular treatment-emergent adverse event (Section 5.8.8.2) will continue to have examinations every 2 weeks until the condition resolves or is deemed to be irreversible by the investigator.
- Concomitant medications(Appendix A and Appendix B)
- Directed neurological examination will be performed, to include light touch, pinprick, proprioception, and deep tendon reflexes (DTRs) of the upper and lower extremities; and questioning for symptoms of paresthesia and numbness. If abnormal, an NCI CTAE grade will be recorded and if warranted a neurologist will be consulted (Appendix A and Appendix B)
 - o Neurotoxicity Questionnaire (FACT/GOG NTx), Version 4.0 (Appendix G)
- HAHA and HADA sample collection as outlined in Section 6 and Appendix C

All serious adverse events, and those adverse events assessed by the Investigator as at least possibly related to study drug should continue to be followed until they resolve or stabilize, whichever comes first.

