- a. Within 28 days prior to the start of Cycle 1, Day 1
- b. Directed physical examination is acceptable while on study treatment. Full examination is required at screening and the 28-Day Follow Up visit.
- c. Within 14 days prior to the start of Cycle 1, Day 1
- d. Vital signs (blood pressure, pulse, respiration rate, and temperature) will be measured as outlined in Section 8.6 and 8.7.
- e. Pulmonary Function Tests will be performed within 14 days of receiving the first dose of study treatment (Cycle 1 Day 1) and as clinically indicated.
- f. Day 1 laboratory assessments may be performed up to 4 days prior to study agent administration. Laboratory results must be reviewed prior to each scheduled administration of IMGN853. In the event of severe toxicity, repeat laboratory tests should be performed as necessary until the toxicity resolves or stabilizes. For a complete list of laboratory assessments, refer to Section 8.10.
- g. For WCBP, a urine or serum pregnancy test will be performed at screening, prior to dosing on Day 1, every-other-cycle while on study and at the 28-day Follow-Up visit. Additional testing may be performed in accordance with institutional requirements or local regulation.
- h. Baseline ophthalmic exams will be performed by a board-certified ophthalmologist and will include the following: indirect fundoscopy, slit lamp examination under dilatation, intraocular pressure measurement, and corneal photography. A Schirmer test will be performed at baseline for all patients, and for patients who experience ocular symptoms, it will be repeated at the first on-study ophthalmic examination and at subsequently if clinically indicated. The baseline exam may be performed within 14 days of Cycle 1, Day 1. Ocular symptom assessment will be performed prior to the start of each cycle by the treating physician or other qualified individual. If the subject reports ocular symptoms then IMGN853 will be stopped and the subject will then be referred to an ophthalmologist for a complete examination (Section 5.8.8).Patients who experience ocular toxicity will have a complete ophthalmologic exam performed every other cycle, including patients with blurred vision but normal eye examinations. All patients will have a complete ophthalmologic exam performed at the End of Treatment visit or 28-Day Follow Up.

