6.10. Ophthalmic Examinations

Results of the Ophthalmic Examinations will be presented in data listings.

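### The End of Treatment eye examination in Protocol 10.7 conflicts with Table 7, 10.8 and Appendices A/B, and symptom-triggered examinations can bias recorded keratopathy in favour of the steroid drops because the SAP only lists the universal post-treatment examination

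*Protocol*

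**What the plan says.** The objective at stake is secondary (Protocol 2.3): "Evaluate the effectiveness of primary, prophylactic steroid eye drops in preventing or lessening keratopathy and/or blurred vision".

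The post-treatment eye examination is described in four places:

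- Protocol 5.8.8.1: "Complete ophthalmologic exams and ocular symptom assessments will be performed in all patients at baseline and post-treatment as described in the following schedule". Table 7 defines the complete examination as visual acuity, slit lamp, intraocular pressure and indirect fundoscopy, and marks it at both End of Treatment and 28-Day Follow Up.
- Protocol 10.7, End of Treatment: "Ophthalmic examinations: visual acuity, fundoscopic exam, ocular symptom assessment (Section 5.8.8".
- Protocol 10.8, follow-up at 28 (+14) days after last treatment: "Complete ophthalmic examination for all patients; alternatively, the complete examination can be performed at the End of Study visit".
- Appendix A footnote h and Appendix B footnote g: a complete examination for all patients at one of the two visits.

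The baseline content also varies. Table 7 and 10.1 include visual acuity and no corneal photography. The appendix footnotes list "indirect fundoscopy, slit lamp examination under dilatation, intraocular pressure measurement, and corneal photography" and no visual acuity.

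Between baseline and the end of treatment, Table 7 schedules the complete examination every other cycle only for "Patients who report treatment- emergent ocular AEs". The referral rule below the table and section 10.5 work the same way. On Day 1 of each cycle every patient has a symptom assessment only.

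SAP 6.2 tabulates keratopathy and blurred vision as ocular TEAEs, with onset up to 28 days after the last dose. For the examinations themselves, SAP 6.10 says: "Results of the Ophthalmic Examinations will be presented in data listings".

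**The concern.** Keratopathy is a corneal finding, and the slit lamp is the component of the complete examination that looks at the cornea. During treatment a patient reaches the slit lamp by reporting an ocular symptom or having an ocular adverse event recorded. Cohort 5 receives drops that are meant to reduce such symptoms. If the drops work on symptoms, fewer Cohort 5 patients are examined and fewer corneal findings are recorded, even if the cornea is no better protected. A comparison of keratopathy TEAE rates with patients who did not use drops would then favour the drops through detection alone.

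The safeguard is the examination that every patient should have after treatment. It is weakened in three ways. Section 10.7 does not name the component that matters. The documents disagree on whether the examination is due at one visit or two. Its results are never summarised. In addition, when it is done at follow-up on days 29 to 42, a finding given that date as onset falls outside the 28-day TEAE window and so outside the ocular TEAE tables.

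**Working it through.** **The plan's only figure on ocular benefit.** Protocol 11.1 gives 68% power for a fall in blurred vision from 50% to 30%, with 40 patients, one-sided alpha 20% and a chi-square test. With the pooled two-sample formula, power = Φ[(d − z·√(2p̄(1−p̄)/n)) / √((p₁q₁+p₂q₂)/n)], where d = 0.20, p̄ = 0.40 and z = 0.8416:

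- 20 per group (40 in total): (0.20 − 0.8416 × 0.1549)/0.1517 = 0.459, which gives 67.7%.
- 40 per group: (0.20 − 0.8416 × 0.1095)/0.1072 = 1.005, which gives 84.3%.

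The figure reproduces with 40 as the total. It concerns a symptom, not keratopathy, and is not disputed here. It supplies the 50% and 30% used below.

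**Content of the End of Treatment examination, side by side.** Table 7 has four components: visual acuity, slit lamp, intraocular pressure, fundoscopy. Section 10.7 names two of the four, visual acuity and fundoscopy, plus the symptom assessment. Its line cites 5.8.8, so a site could read it either as the short list or as the full Table 7 examination. Section 10.8 names End of Study as the alternative visit, while the appendix footnotes name End of Treatment. I take these to be the same visit.

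**Timing.** Follow-up is due on days 28 to 42 after last treatment, and TEAE onset must be within 28 days of the last dose. That leaves days 29 to 42 uncovered.

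**Size of the detection effect.** Assumptions that the documents do not supply: the true keratopathy rate K is the same with and without drops and independent of symptoms; symptoms trigger an examination in a fraction s of patients, 0.50 without drops and 0.30 with (the planning rates for blurred vision); a triggered examination finds keratopathy if it is there; and e is the chance that symptom-free keratopathy is found and counted at the universal post-treatment examination.

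Recorded rate = K × [s + (1 − s) × e], so the apparent risk ratio = (0.30 + 0.70e)/(0.50 + 0.50e), and K cancels.

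| e | With drops / without | Apparent risk ratio | Chance that a one-sided 20% chi-square test favours the drops, 40 v 40, K = 0.3 to 0.6 |
|---|---|---|---|
| 0 | 0.300 / 0.500 | 0.60 | 51% to 66% |
| 0.25 | 0.475 / 0.625 | 0.76 | 40% to 51% |
| 0.50 | 0.650 / 0.750 | 0.87 | 31% to 40% |
| 1.00 | 1.000 / 1.000 | 1.00 | 20% to 22% |

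The last column sums exact binomial probabilities. It is illustrative only, since the plan specifies no test for keratopathy. With no true effect it should be near 20%, and it is when e = 1.

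**The case against.** The strongest reply is that nobody is left unexamined. Table 7, 10.8 and the Appendix A/B footnotes each give every patient a complete post-treatment examination, 10.7 itself refers to 5.8.8, and only a complete examination can stand in for the one at follow-up. This stands. A reader might infer from 10.7 that symptom-free patients have no slit lamp after baseline and that their keratopathy goes unseen. The documents do not support that. What can be missed is keratopathy that arises and clears during treatment without symptoms.

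A reader might also take the first row of the table as the answer: a 40% apparent reduction, with 40 − 0.30 × 40 = 28 of 40 Cohort 5 patients depending on one examination. That needs e = 0, which contradicts the universal examination. It also equates blurred vision with the trigger, which is any ocular symptom of any grade. Independence is a further strong assumption, because 5.8.8.1 describes visual acuity changes that result from keratopathy.

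Other points reduce the weight without removing the concern:

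- Reversibility is reported in 5.8.8.1 for other DM4 conjugates with the SPDB linker, and IMGN853 uses sulfo-SPDB (1.4.3.3). How quickly corneal findings clear here is not stated.
- Section 9.1.1.1 allows adverse events to be found by examination, so a symptom-free finding within 28 days can still enter the TEAE tables.
- Slit lamp appears in every baseline list, so the baseline mismatch affects visual acuity and photography only.
- The study tests no formal hypothesis, and blurred vision, the quantity in the power statement, is asked of every patient on Day 1 of each cycle.

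**Conclusion.** The conflict between 10.7 and Table 7, 10.8 and the appendix footnotes is plain on the page. The ascertainment bias is real in direction: on-treatment slit-lamp examination depends on something the drops are meant to change. It affects only the keratopathy part of the objective.

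The documents do not fix its size. Under equal true keratopathy independent of symptoms, and triggers in 50% versus 30% of patients, the apparent risk ratio runs from 0.60 to 1.00 as detection at the universal examination goes from none to complete. The lower end should not be quoted alone, because the plan does provide that examination. The weakness is that its content and timing are stated inconsistently and the SAP does not use it beyond a listing. This is worth correcting because the correction is cheap. Making End of Treatment the only permitted time point would be a preference: that visit is tied to the decision to stop treatment (within 7 days), whereas follow-up is tied to the last dose.

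**What to change.** In the protocol, reconcile 10.7, 10.8, Table 7, 10.1 and the Appendix A and B footnotes, so that the post-treatment examination that counts for every patient is the Table 7 complete examination including slit lamp. State whether it is due at one visit or both, and use one component list at baseline.

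In SAP 6.10, add a table of slit-lamp corneal findings at baseline versus the universal post-treatment examination, for all treated patients by cohort, whatever the day of that examination. Show the number of examinations per cohort, and show symptom-triggered findings separately. Report this beside the ocular TEAEs for the keratopathy part of the steroid-drop objective.

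Cost: text alignment and one extra table, with no procedure beyond those in Table 7. SAP 1.1 allows changes until database lock, so the table can be added even if visits are complete. It limits the bias but does not remove it, because keratopathy that resolves during treatment without symptoms would still be missed. The report should say so.

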10.8. Follow-up Assessments

Safety Follow-up: A safety follow-up visit will occur 28 days (+ 14 days) after the last treatment. During this visit, the following assessments will be performed.

- Complete physical examination (Appendix A and Appendix B)
- Vital signs (Section 8.6, Appendix A and Appendix B)
- Pulse oximetry (Section 8.8)
- Weight (Appendix A and Appendix B)
- ECOG performance status (Appendix A and Appendix B)
- 12-Lead ECG (if clinically indicated)
- Pregnancy test for WCBP (Appendix A and Appendix B)
- Clinical laboratory tests (Section 8.10, Appendix A and Appendix B):
 - Serum chemistry
 - Hematology
 - Coagulation profile
 - Urinalysis
- Radiologic imaging to monitor tumor response if PD has not been documented already (Appendix A and Appendix B)
- For patients with EOC, uterine cancer or NSCLC only:
- CA125 for patients with EOC, primary peritoneal cancer, fallopian tube cancer or uterine cancer (Appendix F)

NOTE: patients experiencing CA125 response must have a confirmatory test performed at least 28 days after initial response is documented.

- AEs and SAEs (Appendix A and Appendix B)
- Ocular symptom assessment (Section 5.8.8)

ImmunoGen, Inc. Confidential Page 104 of 138

- Complete ophthalmic examination for all patients; alternatively, the complete examination can be performed at the End of Study visit.
 - Patients experiencing an ocular treatment-emergent adverse event (Section 5.8.8.2) will continue to have examinations every 2 weeks until the condition resolves or is deemed to be irreversible by the investigator.
- Concomitant medications(Appendix A and Appendix B)
- Directed neurological examination will be performed, to include light touch, pinprick, proprioception, and deep tendon reflexes (DTRs) of the upper and lower extremities; and questioning for symptoms of paresthesia and numbness. If abnormal, an NCI CTAE grade will be recorded and if warranted a neurologist will be consulted (Appendix A and Appendix B)
 - o Neurotoxicity Questionnaire (FACT/GOG NTx), Version 4.0 (Appendix G)
- HAHA and HADA sample collection as outlined in Section 6 and Appendix C

All serious adverse events, and those adverse events assessed by the Investigator as at least possibly related to study drug should continue to be followed until they resolve or stabilize, whichever comes first.

Response Follow-up: Patients who have discontinued study treatment for reasons other than PD will be followed per Revised Response Criteria (RECIST 1.1, see Appendix E) every 12 weeks (+/- 3 weeks) until documentation of PD, or until the patient starts subsequent anti-cancer therapy, whichever comes first.

ImmunoGen, Inc. Confidential Page 105 of 138

11. STATISTICAL METHODS

All descriptive statistical analyses will be performed using the most recently released and available SAS statistical software, unless otherwise noted. For categorical variables, the number and percent of each category within a parameter will be presented. For continuous variables, the sample size (n), mean, median, and standard deviation, as well as the minimum and maximum values, will be presented. Missing data will not be imputed unless otherwise stated. There will be a detailed description of patient disposition, patient demographics, and baseline characteristics.

No formal interim analysis is planned for this study. However, a review of safety data and available preliminary PK data will be conducted by the CRC after the MTD or a RP2D for IMGN853 has been determined. Results from this data review could enable selection of dose and dosing schedule for additional studies with IMGN853, before full completion of this study.

A statistical analysis plan (SAP) will fully describe the planned analyses for this trial. All analyses will be performed for any patient that received study drug. All analyses for efficacy will use Cycle 1, Day 1 as the start time.

11.1. Sample Size

Ascending doses of IMGN853 are to be evaluated to identify the MTD for both dosing schedules. The actual number of patients accrued during this phase will be determined largely by the findings observed during the course of their treatment.

Following identification of the MTD for Schedule A (Q3W), there was an expansion phase which initially accrued two cohorts at the MTD: (1) Dose Expansion Cohort 1-40 patients with platinum resistant EOC. (2) Dose Expansion Cohort #2-20 patients with advanced or recurrent uterine cancer. Once the Schedule B MTD (modified weekly) was established, the CRC convened to review safety, PK and efficacy results from the both schedules as well as preliminary data from the Expansion Cohorts 1 and 2, with the Q3W schedule of administration. The CRC recommended use of Schedule A for all future cohorts. Three additional MTD Expansion Cohorts will enroll the following patients: (3) Dose Expansion Cohort 3-20 patients with relapsed ovarian cancer, which is amenable to biopsy (4) Dose Expansion Cohort 4-20 patients with relapsed/refractory NSCLC adenocarcinoma, and (5) 40 patients with platinum resistant EOC who will receive daily treatment with corticosteroid-containing eye drops.

If the true DLT rate at the MTD is 10-20%, there is an 98.5-99.9% probability of observing at least one DLT in each 40 patient cohort. If the true response rate at the MTD is 20%, there is a 99.9% probability of observing at least one response in each 40 patient cohort.

ImmunoGen, Inc. Confidential Page 106 of 138

x (Number	True Event Rate			
Observed)	10%	20%	30%	
1	0.985	0.999	0.999	
2	0.919	0.998	0.999	
3	0.777	0.992	0.999	
4	0.577	0.972	0.999	
5	0.371	0.924	0.997	
6	0.206	0.838	0.991	

Table 16: Probability of Observing $\geq x$ Events (Response or DLT) For a 40 patient Cohort

Given a sample size of 40 patients, the power to detect a difference of 20% (rate of Blurry vision decrease from 50% to 30%) is 68% using one-sided alpha of 20% and Chi-Square test statistics.

Safety will be evaluated continuously, separately, and in aggregate in the expansion cohorts. If at any time ≥ 33% of patients treated in an expansion cohort experiences a Cycle 1 DLT, further enrollment to that cohort will stop and a CRC will be convened. The CRC will review all available safety data and PK data to determine how further dosing should proceed. If the CRC determines that the dose should be revised during the expansion phase for a given expansion cohort, that cohort will enroll additional patients at the revised dose to fulfill the enrollment goal.

Approximately 209 patients will be enrolled in the study, allowing for dropouts and expansion of dose escalation cohorts as needed.

